13.3 Efficacy Outcomes

Comparisons of the TCG and SCG groups will be made with regard to the following: (1) participant engagement in aftercare programs and (2) drug and alcohol use abstinence at 13 weeks post-discharge. We believe that those who receive the telephone calls during the post-discharge period will have better compliance with aftercare programs and a higher drug/alcohol abstinence rate at the follow-up visit than those who do not receive calls.

The main efficacy measures will be—

- Self-reported engagement in aftercare activities prescribed in the continuing care plan prepared by the residential treatment program, derived from the number of treatment and self-help activities the patient engaged in/attended during the 13-week post-discharge period
- Drug use as measured by urine test
- Alcohol use as measured by breath alcohol test

Self-report measures that will be examined as part of a supplemental analysis include—

- Drug and alcohol use during the past 30 days as measured by the CTN ASI-Lite forms
- Other measures of functioning from the CTN ASI-Lite forms
- HIV and HCV risk behaviors as measured by the HIV Risk Behavior Survey (RBS)
- Client satisfaction with the continuing care plan, as measured by the 13
 Week Continuing Care Compliance form

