Prior to their planned discharge (as close as possible to the date of the participant's planned discharge, ideally within the 2 business days prior to the planned date of discharge or on the actual day of discharge), consenting participants who have met all eligibility requirements for the study will be randomly assigned to one of 2 post-discharge conditions: standard of care group (SCG) or SCG plus 7 scheduled telephone calls (TCG) placed during the first 87 days after discharge. We believe that TCG participants will have greater participation in continuing care activities and that a higher proportion will be abstinent from drugs and alcohol at the time of a follow-up visit, as compared with those in the SCG. Information on participation in continuing care activities (measured by self-report and verification with post-discharge programs), drug/alcohol use (documented by urine tests and breath alcohol tests), and a battery of other measures will be collected at the 13-week follow-up visit for all randomized participants.

Study results will be aggregated across sites and examined within individual sites.

The experience gained through the implementation and operation of this protocol will provide the data necessary to justify a future multi-site trial. If the TELE procedure is ultimately found to be efficacious in a full-scale trial, this work will represent one model for bringing current community-based clinical practice, which has not been extensively evaluated, into the CTN for rigorous empirical examination.

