Randomization will be performed at each participating residential program by using a randomization sequence developed by the statistician at the Lead Node and provided in sealed, sequentially numbered envelopes to the participating centers. A stratified randomization with permuted blocks will be employed. The randomization scheme will stratify by site (residential program) in order to maintain an approximate balance between treatment groups at each site.

For the TCG participants, calls will be made during weeks 1, 2, 4, 6, 8, 10, and 12 after discharge from residential care. Telephone calls will focus on the participants' self-reported adherence to the continuing care plan that was provided to them at discharge. Contact success and duration of all calls will be documented. A portion of calls will be recorded and at least 10% of successful calls will be randomly selected and scored for fidelity to the intended call procedures.

Participants in each group will be assessed for treatment effects at a follow-up visit expected to occur at 13 weeks after discharge from the residential setting. Day of discharge will be considered as day 0 of follow-up. The window for this visit will be from days 88–116 following discharge from the residential program.

During the study, data will be reviewed by study monitors utilizing the procedures established by the CTN to assess the completeness and accuracy of data collected.

The analysis of the feasibility and efficacy data will be presented to the Steering Committee for consideration in their decision on whether to conduct a larger, multi-site trial.

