10.3.2 Review of the Continuing Care Plan and Randomization

All participants will meet with the TELE counselor prior to randomization as close as possible to the date of the participant's planned discharge, ideally within the 2 business days prior to the planned date of discharge or on the actual day of discharge, to review the continuing care plan. If a thorough review has been performed by the residential program counselor, the TELE counselor only needs to ensure participant comprehension of this plan. Subsequently, the TELE counselor will perform the manual randomization (of participants remaining eligible) to either telephone counseling calls (TCG) or standard of care (SCG). This will be done as close as possible to the date of the participant's planned discharge, ideally within the 2 business days prior to the planned date of discharge or on the actual day of discharge.

A set of envelopes, numbered sequentially and provided to each site prior to the recruitment of participants, will be used to determine a participant's random assignment. At the time of randomization, the TELE counselor will remove the envelope with the next sequential number. Upon opening the envelope, the TELE counselor will inform the participant of the group to which he or she is randomized. If the participant is randomized to SCG, the TELE counselor should remind the participant of his or her planned continuing care and the 13-week visit, and conclude the meeting. If the participant is randomized to the TCG, the TELE counselor should schedule the first call during this meeting. The participant should be reminded of his or her planned continuing care and the week 13 follow-up visit, and the interview should be concluded. Refer to the Counselors Manual for more details.

The goal of this pre-discharge meeting is to establish rapport with all study participants to avoid bias of the study results, which might occur if only the group randomized to follow-up phone calls had had the pre-discharge meeting.

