10.6.2 Verification of Continuing Care Compliance after Follow-up Visit

After completion of the 13-week follow-up visit, participation in continuing care will be verified, where feasible, by confirming attendance/participation in the assigned program as identified on the continuing care (discharge) plan.

In order to verify this information, participants will be asked to sign a program-specific release form at the pre-discharge interview. If the participant attended a program that was not specified on the continuing care plan, an additional program-specific release form will be obtained during the follow-up visit. Attendance and participation in at least one counseling session will be recorded on the follow-up CRF.

Additionally, if approved by the local IRB, the research staff may confirm the participant's self-reported information on criminal justice activity by using the release signed at the pre-discharge interview and/or reviewing public records (e.g., court records, arrest logs, probation and parole records).

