10.6.3 Verification of Continuing Care Compliance for Missed Follow-up Visit

If the follow-up visit is missed (e.g., the participant is a 'no-show'), the research staff will use release forms signed at the pre-discharge interview to verify attendance and

participation in the continuing care activities as identified in the residential program's continuing care plan. Additionally, if approved by the local IRB, the research staff may use the release signed at the pre-discharge interview to verify self-reported criminal justice activity that occurred after discharge from the residential facility.

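### Section 13.3 measures engagement by unblinded self-report only and gives the planned program verification of attendance no role in the analysis

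*Protocol*

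**What the plan says.** Section 13.3 lists as a main efficacy measure "Self-reported engagement in aftercare activities prescribed in the continuing care plan prepared by the residential treatment program". The measure is based on a count over the 13 weeks after discharge and takes in self-help as well as treatment. Section 5.2 also names self-reported engagement. The supplemental measures in 13.3 contain no verified attendance either.

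The synopsis (section 3.0) describes participation in continuing care as "measured by self-report and verification with post-discharge programs".

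The verification procedure is set up elsewhere:

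- Section 10.3.1: releases for the programs to which the participant is referred are signed at the research assistant's meeting, before randomization.
- Section 10.6.2, after an attended visit: "participation in continuing care will be verified, where feasible, by confirming attendance/participation in the assigned program as identified on the continuing care (discharge) plan". It adds: "Attendance and participation in at least one counseling session will be recorded on the follow-up CRF". A further release is taken at the visit if the participant went to a program not on the plan.
- Section 10.6.3, after a missed visit: "the research staff will use release forms signed at the pre-discharge interview to verify attendance".
- Table 3 (section 11.12) lists a Verification Form.

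On blinding, section 10.3.2 states that "the TELE counselor will inform the participant of the group to which he or she is randomized". Section 8.0 says that the calls, made to one arm only, focus on participants' "self-reported adherence to the continuing care plan that was provided to them at discharge".

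**The concern.** The first research question is whether the calls lead people to take up the care in their discharge plan. Only the call arm is asked, up to seven times, how well it is keeping to that plan. At week 13 participants in both arms, knowing their allocation, report the same behaviour as the outcome. If call-arm participants who did not attend are more ready to say that they did, the result looks like benefit.

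Self-report also requires the week-13 interview, so it is absent for those who miss it, although section 10.8 says that all randomized participants will be included in the analysis.

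What makes this worth changing is that the protocol already plans to collect a more objective record, including for no-shows, and then does not analyse it. For substance use the protocol does the reverse: urine and breath tests are main measures and self-reported use is supplemental.

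The stake is the effect size. Section 5.1 lists it among the critical feasibility aims because future power calculations will need it, and sections 13.2 and 13.3.1 repeat that use. An inflated engagement effect would lead to a full trial that is too small.

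**Working it through.** **1. The passages side by side**

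| Place | How engagement is measured |
|---|---|
| 3.0 Synopsis | Self-report and program verification |
| 5.2 Efficacy | Self-report |
| 10.6.2 (visit attended) | Verification where feasible; one or more counseling sessions recorded |
| 10.6.3 (visit missed) | Verification through pre-discharge releases; recorded item not named |
| 13.3 Efficacy Outcomes | Self-reported count, including self-help; verified record not used |

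Section 3.0 does not agree with 5.2 and 13.3, and nothing in section 13 takes up the output of 10.6.2 and 10.6.3.

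**2. The sample size used below**

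Section 13.5 sets 360 from practical constraints, not power. It reproduces: 4 sites × the midpoint of 60 to 120 = 4 × 90 = 360. The accrual figures agree: 16 × 0.75 = 12, 12 × 0.85 = 10.2, or about 10 per month per site, and 4 × 10 × 9 months = 360. Section 3.0 gives 180 per arm.

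**3. Missing self-report**

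Section 13.3.1 anticipates that 20% or fewer will be missing at follow-up. At 20%, 0.20 × 360 = 72 have no self-report and 288 remain, or 144 per arm if loss is equal.

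How many of the 72 verification would recover is not stated. Assumed range:

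| Share of missed visits verified (assumed) | Participants with engagement data |
|---|---|
| 0% | 288 |
| 25% | 288 + 18 = 306 |
| 50% | 288 + 36 = 324 |
| 100% | 288 + 72 = 360 |

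For a yes/no outcome with 50% attending (assumed), the 95% interval half-width for the difference is 1.96 × √(2 × 0.5 × 0.5 / n). This is 11.5 points at n = 144 per arm and 10.3 points at n = 180. The gain in precision is modest. The larger gain is that no-shows are no longer left out by design.

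**4. Reporting bias, as an illustration**

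All rates here are assumed. With no true effect,

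spurious difference = (1 − true attendance) × excess over-reporting among call-arm non-attenders.

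At 50% true attendance: 0.5 × 0.10 = 5 points and 0.5 × 0.20 = 10 points.

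To put this against sampling error, take 144 per arm and let 10% of control-arm non-attenders over-report. At 50% attendance and 10 points of excess, the reported rates are 0.5 + 0.5 × 0.10 = 55% and 0.5 + 0.5 × 0.20 = 60%. The table gives the spurious difference and, in brackets, the chance of a nominal two-sided p < 0.05 favouring the calls.

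| True attendance | Excess 5 points | Excess 10 points | Excess 20 points |
|---|---|---|---|
| 30% | 3.5 (9%) | 7 (23%) | 14 (67%) |
| 50% | 2.5 (6%) | 5 (14%) | 10 (41%) |
| 70% | 1.5 (5%) | 3 (8%) | 6 (22%) |

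Unbiased reporting would give 2.5% in that direction. The table treats the outcome as yes/no, whereas 13.3 derives it from a count, so it shows the order of the problem and not the behaviour of the planned test.

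**The case against.** The strongest defence is that the two records measure different things. Section 13.3 wants the number of activities, self-help included. The one verified item that the protocol names is a threshold of a single counseling session, and no way of verifying self-help is described. Someone who attended self-help throughout and no formal program would count as a non-attender. Self-report is the only described source that covers the stated outcome. This stands, and it rules out the inference that verified attendance should replace the self-reported count.

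A reader might also infer that verified attendance will exist for everyone, so that the missing data are fully avoidable. The documents do not support that. Verification is qualified as where feasible, depends on releases, and covers named programs. Section 10.6.3 does not say which item is recorded for no-shows.

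Relying only on pre-discharge releases has its own risk. If the calls help people find a program that was not on the plan, those people would look like non-attenders and the comparison would lean against the calls. That is a reason for a sensitivity analysis.

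There are safeguards. The research assistant, not the calling counselor, collects the week-13 data. Both arms meet the counselor before discharge. Call content is not used as research data apart from serious adverse events. These limit some biases, but they do not remove the call arm's repeated prompting on the behaviour later self-reported.

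Finally, efficacy is secondary, is acknowledged to be underpowered, and has no predefined significance level. This lowers the weight of any false-positive argument. It does not help with a biased effect size, which is the product wanted from this analysis. That the two missing-data approaches in 13.3.1 are stated for abstinence only is not itself a fault, since engagement may be covered in an analysis plan that is not shown.

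**Conclusion.** The point holds as a cheap improvement to an exploratory analysis. Section 13.3 rests engagement on unblinded self-report, disagrees with the synopsis, and leaves an already planned, more objective record without a role.

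Up to 72 of 360 participants would lack the measure if loss reaches 20%. Verification could recover an unknown part of them.

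A reader might take the 5 to 10 point spurious difference as an estimate of the bias in this trial. It is not: it follows from an assumed 50% attendance and an assumed 10 to 20 points of excess over-reporting. With 5 points of excess it is 1.5 to 3.5 points over the attendance range examined. The documents support the direction of the risk, not its size.

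**What to change.** Reconcile sections 3.0, 5.2 and 13.3, and add a second engagement outcome to 13.3:

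- **Outcome.** Verified attendance at one or more counseling sessions (yes/no) at programs named on the continuing care plan, compared by arm in all randomized participants with the test for proportions already in 13.3.1. The self-reported activity count stays beside it.
- **Ascertainment.** Base the comparison on releases signed before discharge, so that the set of programs is fixed before allocation and is the same for attended and missed visits. State in 10.6.3 that the item named in 10.6.2 is also recorded for missed visits.
- **Sensitivity analysis.** Add programs released at the follow-up visit, noting that these exist only for participants who attended it.
- **Unverifiable programs.** Keep a separate category for attendance that could not be verified; do not silently count it as non-attendance.
- **Reporting.** By arm, give the share of participants whose attendance could be verified and the agreement between the verified record and self-report. Different agreement in the two arms would be direct evidence on differential over-reporting.

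The cost is wording and a few tables, since the releases and verification are already planned. The limit is that the verified outcome covers formal treatment only and says nothing about self-help or the amount of attendance.

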13.3.1. Analysis of the Efficacy Outcomes

The efficacy analyses will be used to guide future research and provide preliminary data to estimate the effect size and required sample size for a clinical trial. To this end, descriptive statistics will be presented for each outcome as described in Section 13.1. Although the main goal of this study is to evaluate feasibility, a set of hypothesis-testing methods will be applied to provide a preliminary evaluation of the treatment effects. The later analysis will provide a preliminary overview of the clinical effectiveness of the regimen of telephone calls. Information from this study can then be used to inform the design of a full-scale clinical trial of the TELE protocol.

The results of the following hypothesis-testing procedures should be used to guide future research plans rather than to draw definitive conclusions regarding the relative effectiveness of the 2 treatment conditions. In the case of a binary outcome (e.g., abstinence or non-abstinence), tests for differences in proportions will be performed to examine between treatment group differences. A student's *t*-test for independent groups will explore between-group differences on continuous outcome measures. If continuous data violate the assumption of normality, the Wilcoxon rank-sum test will be used to

compare groups. For each of these 2-tailed statistical tests, a *P* value will be presented. However, there will be no predefined level of significance established for the present study due to its exploratory nature.

Outcome measures will be analyzed for the entire study population. Descriptive statistics will be presented for each outcome. The analysis will be conducted to investigate the characteristics of the variables from each site prior to combining data from multiple sites. Comparisons will be between the SCG and TCG performances both within each site and across sites.

Equality of treatment groups at baseline will be evaluated by comparing demographic and drug-use information collected on the CTN ASI-Lite Version 1 and Follow-up forms. Baseline demographic values that potentially affect the responses or are found to be unevenly distributed between groups at baseline despite randomization may be investigated in supplementary analyses. Baseline values are not planned to be covariates in any analyses because sample sizes are expected to be too small. Where possible, treatment effects will be summarized by gender, ethnicity, and age group separately.

A summary will be prepared to show dropouts/retention over time in each treatment group. The number of missing observations will be compared between treatments. In the analysis of the effect of the telephone call regimen on the participant abstinence (objective measure by urinalysis & breathalyzer), participants lost to follow-up at 13 weeks will be handled in 2 different approaches in an attempt to elucidate the influence of missing data on interpretation of the results. In the first analysis, participants lost to follow-up at 13 weeks will be considered "non-abstinent" to account for the possibility that non-abstinent participants may be more likely to be lost at follow-up. In the second approach, participants lost to follow-up at 13 weeks will be considered as missing. We anticipate that the category "missing at follow up" will account for 20% or fewer of randomized participants. Effects of gender and substance use diagnosis will be investigated in a supplementary analysis.

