In the feasibility study, 4 sites will conduct the procedures outlined in this protocol. Procedures have been designed by the TELE protocol group and approved by the Clinical Trials Network (CTN) Steering Committee. The feasibility study will include 360 randomized participants—180 per treatment condition. Each of the sites is expected to randomly assign 60 to 120 participants. If the study shows that it is feasible to deliver the telephone calling intervention and to collect adequate data to compare with a control group, and there is evidence to suggest positive effects of the intervention, recommendations will be made to the CTN Steering Committee for a large-scale trial evaluating the efficacy of the TELE procedure.

The feasibility study will be conducted as follows:

Candidates eligible for randomization will include men and women enrolled in residential substance abuse treatment programs for at least 7 days but no more than 42 days. Participants must be at least 18 years of age and have the ability to understand and provide written informed consent. In addition, they must have been voluntarily admitted (not civilly committed) to the rehabilitation regimen (not admitted for detoxification only) and have a diagnosis for substance abuse or dependence as determined by residential program admission information. Referrals must be from a program servicing the targeted counties at the time of admission, and participants must plan to return to residence in the target counties after their discharge from the residential treatment program. Participants must have no evidence of current suicide intention or recent (\leq 30 days prior to admission) suicide attempt and must complete study requirements prior to departure from the program. All participants must have a working telephone number for contact after their discharge.

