5.0 STUDY OBJECTIVES

5.1 Feasibility

The primary objective of this clinical investigation is to evaluate the feasibility of a randomized clinical trial testing the use of a telephone call support (TELE) procedure to enhance continuing care activities after completion of residential treatment programs for substance abuse. Several aspects of this feasibility study are equally important and failure to complete them would indicate the need for serious reconsideration or restructuring of a future full-scale TELE protocol. The critical aspects of feasibility in this study are listed below:

- 1. Determining the proportion of the total eligible participants who volunteer to participate in the study
- 2. Obtaining informed consent on an adequate number of newly admitted residential treatment patients for participation in the study
- 3. Determining the proportion of consented participants who complete all required residential treatment and data collection activities and are randomized into one of the 2 study conditions
- 4. Determining whether it is possible to contact this population via telephone after they have been discharged from residential substance abuse care
- 5. Determining how many of the 7 scheduled calls in the group randomized to the TCG actually have the intervention delivered
- 6. Determining whether counselors who deliver the calls can be trained to conduct these calls in a standardized manner using a structured "script"
- 7. Determining the magnitude of the "effect size" within such a design (This information will be needed in power calculations for any future study.)
- 8. Determining whether adequate data (i.e., sufficient and equivalent follow-up data), which would be required in an adequately powered multi-site trial, are collectible in typical community-based treatment organizations after participants leave the treatment setting

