13.5 Sample Size Estimate

Because this is a feasibility study, we had 3 major considerations: to complete the study in a timely manner, to keep the costs low, and to recruit as many participants as possible within these constraints. Thus, rather than statistical power guiding the sample size decision, real-life research constraints were invoked. In terms of study timeline, the duration of enrollment is anticipated to be 9–12 months in order to give the CTPs ample time to become familiar and competent with the study protocol, so that in addition to

months reflecting start-up, we would have data for several months that reflect the full potential of the CTPs to recruit participants. Each CTP is expected to randomize about 60 to 120 participants across the recruitment period. Thus, 360 participants are estimated for the total sample size across CTPs.

Not all individuals who agree to participate will complete their residential treatment episode, and an additional number will fail to meet the eligibility criteria for the study. Based upon program experience, we expect approximately 25% of participants to fail to complete their residential treatment, and an additional 15% to fail to meet the eligibility criteria of the study. Thus, if 16 participants per month agree to participate, we would expect 12 to complete their residential treatment, and approximately 10 to meet the eligibility criteria of the study. Based on these numbers, we expect that approximately 4 participants per week will agree to participate at each CTP (at intake to the residential program).

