13.7 Randomization

Randomization (1:1 treatment allocation) will be performed using a randomized block design, stratified by site. This will enable sites to enroll differing numbers of participants while maintaining a fairly close balance between groups within sites. One of the outcomes of this feasibility study is the measure of whether the CTPs are capable of enrolling the expected numbers. Thus, some of the CTPs may not enroll the expected number, and we will employ blocking in order to preserve our ability to examine existent data at the end of the study. Block size will be determined by the statistical group at the Lead Node who will prepare the randomization scheme.

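### Randomization is stratified by site, but the combined between-arm tests in 13.3.1 carry no site stratum and no confidence interval is named for the between-arm difference

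*Protocol*

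**What the plan says.** **Design.** Section 8.0 states that "The randomization scheme will stratify by site (residential program) in order to maintain an approximate balance between treatment groups at each site". Section 13.7 repeats it: "Randomization (1:1 treatment allocation) will be performed using a randomized block design, stratified by site". The Synopsis (3.0) gives the size: "The feasibility study will include 360 randomized participants—180 per treatment condition". There are four sites, and 13.5 adds that "Each CTP is expected to randomize about 60 to 120 participants across the recruitment period".

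**Tests.** Section 13.3.1 fixes the between-arm methods. For binary outcomes, "tests for differences in proportions will be performed to examine between treatment group differences". Continuous outcomes get a Student's t-test for independent groups, replaced by the Wilcoxon rank-sum test if normality fails. "For each of these 2-tailed statistical tests", the protocol promises a P value and sets no significance level. Site data are inspected before they are combined, and the arms are compared both site by site and overall. Section 13.6 lists site effects only as a possible post hoc topic.

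**Intervals.** Section 13.1 attaches 95% limits to means and proportions, across sites and by site, and says they are there to inform a larger trial. Section 13.3.1 applies these descriptive statistics to every efficacy outcome. No section names an interval for the difference between arms.

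**Purpose.** Objective 7 in 5.1 is the magnitude of the effect size, and the protocol explains that "This information will be needed in power calculations for any future study".

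**The concern.** Two features of the stated method fit the design and the objective poorly.

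First, blocking within site balances the arms on site, so between-site variation largely drops out of the arm difference. A test that treats the combined data as two simple independent samples puts that variation back into the standard error. If sites differ in outcome, the standard error is then larger than the design warrants and the P value is too large.

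Second, the next trial will be sized on the difference between arms. The plan gives limits for each arm and a P value for the contrast, but no interval for the contrast. A sample-size calculation is very sensitive to where the true difference lies, so the uncertainty in that difference is what the planners need to see.

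**Working it through.** **Inputs from the protocol.** 360 randomized, 180 per arm; four sites of 60 to 120; 1:1 allocation blocked by site; at most 20% missing at follow-up (13.3.1).

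**Assumptions.** The protocol gives no outcome rates, site rates, standard deviation or significance level. An average rate of 50%, the site rates below and a nominal two-sided 5% are mine.

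**1. The plan's own figure.** Four sites × 90 (midpoint of 60 to 120) = 360. Also 4 sites × 9 months × 10 eligible per month (13.5) = 360. The total reproduces. It was not set by power, so there is no power figure to check.

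**2. Interval for the difference.** Half-width = 1.96 × √(2p(1−p)/n).
- n = 180, p = 0.5: 1.96 × √(0.5/180) = 10.3 percentage points.
- n = 144 (20% missing): 1.96 × √(0.5/144) = 11.5 points.
- Standardized mean difference: 1.96 × √(2/n) = 0.21 and 0.23.

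The planned per-arm limit at 180 is 1.96 × √(0.25/180) = 7.3 points, and 7.3 × √2 = 10.3. The unadjusted difference interval therefore follows from planned output.

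**3. Why that width matters.** Take 50% in control, 80% power and two-sided 5%, with n per arm = (1.96 + 0.84)² × [p₁(1−p₁) + p₂(1−p₂)]/d². True differences of 20, 10 and 5 points need about 90, 385 and 1,560 per arm. An observed 10-point difference with a half-width of 10.3 is compatible with all three.

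**4. Cost of leaving site out.** The pooled variance uses the average rate, p̄(1−p̄) = 0.25. The stratified variance uses the mean of p(1−p) over sites. The SE ratio is the square root of pooled over stratified. Type I error of the pooled test and of the Cochran-Mantel-Haenszel (CMH) test comes from 200,000 simulated trials per scenario, with equal sites and exact balance within site.

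| Assumed site rates (%) | Mean p(1−p) | SE ratio | Half-width, pooled vs stratified (points) | Pooled test at nominal 5% |
|---|---|---|---|---|
| 50/50/50/50 | 0.2500 | 1.000 | 10.33 vs 10.33 | 5.1% |
| 45/50/50/55 | 0.24875 | 1.003 | 10.33 vs 10.30 | 5.0% |
| 40/45/55/60 | 0.24375 | 1.013 | 10.33 vs 10.20 | 4.9% |
| 30/40/60/70 | 0.2250 | 1.054 | 10.33 vs 9.80 | 3.9% |
| 20/40/60/80 | 0.2000 | 1.118 | 10.33 vs 9.24 | 2.9% |

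The CMH test stayed at 4.9% to 5.1% throughout. Sites of 60/60/120/120 gave nearly the same results; the last two SE ratios became 1.049 and 1.108.

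For a continuous outcome the ratio is 1/√(1 − site share of variance): 1.005 at 1%, 1.026 at 5%, 1.054 at 10% and 1.118 at 20%.

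**5. Cost of including site.** Four sites use 3 degrees of freedom out of 360 participants.

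**The case against.** The strongest reply is that the plan already supplies most of what is needed. A reader of 13.3.1 alone might infer that a P value is the only result reported. That is wrong: the 13.1 descriptive statistics with 95% limits apply to each efficacy outcome, overall and by site. Nor does a switch to the rank-sum test leave nothing to plan on, because means and standard deviations are reported whichever test is used. Site is not ignored either, since it is inspected first and the arms are compared within each site. All of this stands. By-site summaries split by arm would even let someone assemble a stratified difference by hand. What remains is that the plan names no such estimate for the combined data, and the pooled limits cannot yield it.

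A second reply is that the efficacy tests are exploratory, have no significance level and can err only on the conservative side. That also stands, and it keeps the precision point secondary.

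A third is that stratified tests and contrast intervals belong in a statistical analysis plan, and that a test of proportions does not exclude a stratified version. This is fair for the binary outcomes. It is weaker for the t-test and rank-sum test, which are named in unstratified form. Here the protocol has chosen the methods and the output rather than left them open.

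Finally, 13.3.1 omits baseline covariates because samples are expected to be too small. That sentence concerns baseline values and does not mention site, and 3 degrees of freedom out of 360 is not a burden.

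**Conclusion.** The point holds in a limited form. The combined tests leave out the factor by which participants were randomized, and no 95% interval is named for the difference that objective 7 exists to measure. The missing interval is the more useful half: about ±10.3 points at 180 per arm, or ±11.5 with 20% missing, at an assumed rate of 50%.

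The loss from ignoring site is conditional. It is nil if sites are alike, about 1% of the standard error for site rates of 40-60%, 5% for 30-70% and 12% for 20-80%. These spreads are assumptions.

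Two stronger readings should be resisted. One is that the error bars are simply too wide; this is so only if sites differ. The other is that the trial loses 11% to 25% of its effective sample when site explains 10% to 20% of the variance. The loss is 10% to 20%. The larger figures are the extra participants needed to make it up (1/0.9 = 1.11, 1/0.8 = 1.25). Either way the loss lies in the computed standard error: with near-equal arms within each site, the pooled and stratified point estimates are essentially the same. Type I error is not inflated.

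**What to change.** Amend 13.3.1 so that the main between-group output for the combined data is a site-stratified difference with its 95% confidence interval:

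- **Binary outcomes:** Mantel-Haenszel risk difference with its interval, and the CMH test for the P value.
- **Continuous outcomes:** linear model with arm and site, reporting the adjusted mean difference and its interval; van Elteren's test as the rank-based alternative where normality is doubtful.
- **Planning:** state that the next trial will be sized from this interval, not from the P value or the per-arm limits.

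Keep the within-site comparisons and by-site summaries as they are. The change is to wording only. It needs no new data, visits or participants.
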